## 1. Participant Flow

### Recruitment Details

We will choose School of Nursing, Fudan University to recruit the participants. The recruitment will start at May 1st 2020. The recruitment announcement will be distributed to the participants via online notice transmission software used by the school.

### Pre-assignment Details [\*]

We firstly will assess the recruited people to ensure meeting the inclusion and exclusion criteria. Then the final enrolled participants can be sure and randomized assignment will be conducted.

Enrollment (total, anticipatory)	110		Record the number of the eligible and the excluded
Allocation (randomized)	Group A	Group B	Record the number of the received and the unreceived
	55	55	
Follow-up (immediately after intervention)			Record the number of the received and the unreceived

### Arm/Group Information \*

There are two groups in the study.

### Arm/Group Title \*

Intervention group= Group A

Controlled group= Group B

### Arm/Group Description \*§

**Intervention group:** Students will be intervened by an online 5-week professional identity group psychotherapy.

**Controlled group** will receive online messages of self-care knowledge forward by researchers.

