### Started \*

There will be 110 participants initiating the intervention.

Those 110 participants come from two classes in the same grade. One will be randomly allocated as the intervention group, the other will be control group.

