**Outcome Measure Time Frame \***

There will be two measurements, before the intervention and immediately after intervention. They are defined as T0, T1.

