**P-Value [\*]**

P-Value will be set at 0.05.

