**Method [\*]**

- ANOVA
- Chi-Squared
- t-Test, 2-Sided
- Other: repeated measurement of variance analysis within different measurements among different groups

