**Estimation Parameter [\*]**

- Mean Difference (Final Values)

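### The intervention is group psychotherapy, but the listed tests treat the 55 treated students as independent; with several groups and positive within-group correlation, the type I error exceeds 0.05

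*Combined protocol and SAP*

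**What the plan says.** Under Participant Flow, Arm/Group Description, the intervention arm is described so: "Students will be intervened by an online 5-week professional identity group psychotherapy". The control arm "will receive online messages of self-care knowledge forward by researchers". Adverse Event Information, Time Frame, gives five sessions over about 35 days.

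The table under Pre-assignment Details puts 55 students in each group. The Started section says that the students come from two classes in one grade: "One will be randomly allocated as the intervention group, the other will be control group".

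Under Outcome Measure Time Frame: "There will be two measurements, before the intervention and immediately after intervention". Method lists ANOVA, chi-squared, a two-sided t-test and "Other: repeated measurement of variance analysis within different measurements among different groups". On significance: "P-Value will be set at 0.05". The estimation parameter is the difference between arms in mean final score.

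The plan gives no number or size of therapy groups, no ICC or design effect, no group identifier in the data, and no model term for therapy group or class.

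**The concern.** Students in the same therapy group share sessions and interact with each other over five weeks. All four scales are self-reported, so shared experience can plausibly move the scores of a group together. Controls are not grouped by their treatment in this way. The design is therefore partially nested, with treatment-induced clustering in one arm only.

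The listed between-arm tests for the scale scores take students as independent. The repeated-measures ANOVA does not help: it allows for correlation between T0 and T1 within a student, not for correlation between students in the same group.

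At stake are the confidence interval for the mean difference, which would be too narrow, and the error rate, which would be above the planned 0.05. The issue is separate from class-level allocation, because it would remain if students were randomised individually.

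**Working it through.** **Inputs from the plan:** 55 students per arm, significance level 0.05, two-sided test, final-score mean difference.

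**Assumptions (not in the plan):** 10, 7, 5, 3 or 2 therapy groups of nearly equal size; ICC 0.01, 0.05 or 0.10 within therapy groups; equal total variance in both arms. For this first calculation, controls are taken as independent and any class effect is set aside.

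**The plan's own figure.** With ICC = 0, the two-sided 55 v 55 test has type I error 2 × (1 − Φ(1.96)) = 0.050, as stated.

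**Formulas.** With group sizes m:
- design effect in the treated arm, D = 1 + (Σm²/55 − 1) × ICC
- variance ratio, V = (D + 1)/2, since only one of the two equal arms is inflated
- true SE / reported SE = √V
- actual type I error = 2 × (1 − Φ(1.96/√V))

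**Worked example, 5 groups of 11, ICC 0.05.** Σm²/55 = 5 × 121/55 = 11. D = 1 + 10 × 0.05 = 1.50. V = 2.50/2 = 1.25. √V = 1.12. Type I error = 2 × (1 − Φ(1.96/1.118)) = 0.080. At ICC 0.10: D = 2.00, V = 1.50, √V = 1.22, type I error 0.110 (0.1095 before rounding).

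**Type I error over the range:**

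| Groups | ICC 0.01 | ICC 0.05 | ICC 0.10 |
|---|---|---|---|
| 10 (5 or 6 each) | 0.053 | 0.063 | 0.077 |
| 7 (7 or 8 each) | 0.054 | 0.070 | 0.091 |
| 5 (11 each) | 0.056 | 0.080 | 0.110 |
| 3 (18 or 19 each) | 0.060 | 0.102 | 0.152 |
| 2 (27 or 28 each) | 0.066 | 0.129 | 0.199 |

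Simulation of the plain t-test (40,000 trials per setting) agrees. For 5 groups of 11 it gives 0.056, 0.081 and 0.110.

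**Does allowing for therapy group correct this?** For 5 groups of 11, analysing at group level with Satterthwaite degrees of freedom brings the 0.080 and 0.110 back to about 0.055, provided that there is no class effect.

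**What it leaves.** Suppose that there is also a class-level ICC of 0.01 in each arm (assumption). In units of the single-student variance divided by 55, a model that knows the therapy-group variance at ICC 0.05 uses 1.50 + 1 = 2.50. The class effect adds about 55 × 0.01 = 0.55 per arm, so the true variance is 2.50 + 1.10 = 3.60. The ratio is 3.60/2.50 = 1.44, its root is 1.20, and the type I error is 2 × (1 − Φ(1.96/1.20)) = 0.102.

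**The case against.** The strongest case against has four parts.

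1. *The inflation is conditional.* A reader might infer that the error rate certainly exceeds 0.05. The documents do not support that. They state neither the ICC nor whether the treated class is split into groups. At ICC 0 the level is exactly 0.05, and at ICC 0.01 with 5 to 10 groups it is at most 0.056, which is of little practical weight. This stands, and the point has to be read with those conditions.

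2. *Class allocation is the larger defect.* One intact class goes to each arm, so controls are clustered too, and class cannot be told apart from treatment. A reader might infer that a therapy-group term would restore the 0.05 level in this trial. It would not: the calculation above still gives about 0.10 at a class ICC of only 0.01. This also stands. It does not make the therapy-group issue disappear, because correcting the allocation alone would leave the listed tests ignoring the grouping within the treated arm.

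3. *A shared therapist may not matter.* Collection Approach, under Adverse Event Information, mentions the psychotherapist in the singular. If one therapist leads every group, the therapist is constant across the arm and creates no correlation specific to a group. Shared sessions and peer interaction still can.

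4. *The better model is fragile with few groups.* With 5 groups of 11, the between-group variance estimate is zero or negative about 36% of the time at ICC 0.05 and 53% at ICC 0.01. A model that then drops the group term falls back to roughly the uncorrected standard error. This is a reason to specify the degrees of freedom in advance, not to ignore the grouping.

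**Conclusion.** The concern holds in a conditional form. If the 55 treated students are treated in several groups and the within-group correlation is positive, the listed tests understate the standard error and the type I error is above 0.05. The direction does not depend on the group size; the magnitude does.

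Over the assumed range of 10 to 5 groups and ICC 0.01 to 0.10, the true standard error is about 1.01 to 1.22 times the reported one. The effect runs from negligible to about double the stated error rate, and is larger with 2 or 3 groups. These figures isolate therapy-group clustering. They are not the trial's overall error rate, because any class effect comes on top.

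If all 55 are treated as one group, no analysis can separate the group effect from the treatment effect.

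**What to change.** - State the planned number and size of therapy groups, as the intervention is to be delivered. No change of delivery is proposed here.
- Record a therapy-group identifier for every intervention student while the groups run; it may be impossible to reconstruct afterwards.
- For the scale outcomes, replace the independent-sample t-test and ANOVA, and the repeated-measures ANOVA, by a partially nested linear mixed model of the T1 score. It has fixed effects for arm and T0 score, and a random therapy-group effect in the intervention arm only. Use Satterthwaite or Kenward-Roger degrees of freedom, and state that the group-based degrees of freedom are kept if the group variance is estimated as zero. The target remains the difference in mean final score.
- State in the plan that this corrects therapy-group clustering only. The allocation of one whole class per arm needs its own correction. If there is only one therapy group, limit the conclusion accordingly.

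The cost is one data field and revised analysis wording. The statistical price is a wider confidence interval and few degrees of freedom. With 5 groups of 11 at ICC 0.05, the standard error is about 12% larger than the listed tests would report, before allowing for the larger critical value. The ICC will be poorly estimated from so few groups, so little should be read into its value.

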### Period(s) \*

There is only one stage in the study.

### Period Title \*

Overall Study.

### Started \*

There will be 110 participants initiating the intervention.

Those 110 participants come from two classes in the same grade. One will be randomly allocated as the intervention group, the other will be control group.

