## 2. Baseline Characteristics

### Arm/Group Information \*

Chi-square test will be applied to figure out the difference of enumeration data between two groups. ANOVA will be applied to test the difference of measurement data between two groups. F values and  $\chi^2$  values will be displayed to show the baseline data are no different in two groups.

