### Arm/Group Description \*§

Those 110 participants come from two classes in the same grade. One will be randomly allocated as the intervention group, the other will be control group.

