## **5. Limitations and Caveats**

The measurements are mostly based on self-reported scales and may lead to unreliable data. We will give instruction before fulfilling the questionnaire to ensure the participants understood.

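### One intact class per arm: class is completely confounded with treatment, and the planned superiority tests at 0.05 have no valid standard error

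*Combined protocol and SAP*

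**What the plan says.** The unit of allocation is named in two places in the combined protocol and SAP: Started (section 1, Participant Flow) and Arm/Group Description (section 2, Baseline Characteristics). Both carry the same statement: "Those 110 participants come from two classes in the same grade", followed by "One will be randomly allocated as the intervention group, the other will be control group". Pre-assignment Details (section 1) describes an eligibility check and then continues: "Then the final enrolled participants can be sure and randomized assignment will be conducted". It names no unit, and its table shows 55 in each group.

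The intervention is delivered to groups (Arm/Group Description, section 1): "Students will be intervened by an online 5-week professional identity group psychotherapy". The number of therapy groups is not given.

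Section 3 lists superiority and descriptive analysis as the types of test and sets the level at 0.05. The methods listed are ANOVA, chi-squared, a two-sided t-test and "repeated measurement of variance analysis within different measurements among different groups". The estimation parameter is the difference in final means. Nothing in the plan mentions clustering, a class effect or an ICC.

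Section 2 (Arm/Group Information) plans baseline tests whose "values will be displayed to show the baseline data are no different in two groups". The only limitation acknowledged in section 5 is self-report: "The measurements are mostly based on self-reported scales and may lead to unreliable data".

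**The concern.** Two classes in one grade can differ in teachers, timetable, placements, peer climate and prior attainment. Drawing lots between two classes does not balance such differences; it only decides which class's circumstances accompany the intervention. Any difference between the classes that is unrelated to the intervention is counted as treatment effect.

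The listed tests judge the difference against variation between students within a class. That is the right yardstick only if class contributes no variance, and two classes, one per arm, cannot test this. The problem affects every between-group comparison of professional identity, career self-efficacy, stress and resilience, and it cannot be undone once the classes have been allocated.

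**Working it through.** **Inputs from the plan.** Two classes, one per arm (Started); 110 students, 55 per group (Pre-assignment Details); level 0.05 (P-Value); two-sided t-test (Method); difference in final means (Estimation Parameter); measurements at T0 and T1 only (Outcome Measure Time Frame).

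**Assumed.** All ICCs, class differences and correlations below. The plan gives none. It also gives no power, effect size or standard deviation, so the figure of 110 cannot be reproduced.

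**Step 1: degrees of freedom.** Classes − arms = 2 − 2 = 0. Between-class variance cannot be estimated by a mixed model, by a cluster-robust standard error or with larger classes.

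**Step 2: test on final values.** With m = 55 per class and total variance σ²:

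- true variance of the mean difference = 2σ²[ICC + (1 − ICC)/m]
- variance assumed by the t-test = 2σ²(1 − ICC)/m
- ratio R = 1 + m·ICC/(1 − ICC)
- actual type I error = 2·P(t₁₀₈ > 1.982/√R)

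At ICC = 0, R = 1 and the nominal 5.0% is recovered. At ICC = 0.02, R = 1 + 55 × 0.02/0.98 = 2.122, √R = 1.457, and the error is 2·P(t₁₀₈ > 1.361) = 17.6%.

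| Assumed ICC | R | Type I error |
|---|---|---|
| 0 | 1.000 | 5.0% |
| 0.001 | 1.055 | 5.6% |
| 0.005 | 1.276 | 8.2% |
| 0.01 | 1.556 | 11.5% |
| 0.02 | 2.122 | 17.6% |
| 0.05 | 3.895 | 31.7% |
| 0.10 | 7.111 | 45.9% |

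Simulation with 200,000 replicates per value, for ICC 0 and 0.005 to 0.10, agrees to within 0.1 percentage points.

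**Step 3: the same problem as a fixed class difference.** If the two classes differ by d within-class SD for reasons unrelated to treatment, the t statistic is noncentral with noncentrality d√(55/2). For d = 0.1, 0.2 and 0.3 the noncentrality is 0.52, 1.05 and 1.57, and the rejection rate is 8.1%, 18.0% and 34.5%.

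**Step 4: group-by-time test.** With two time points this is a t-test on the change from T0 to T1. A stable class difference cancels; class-specific change does not. Assume a within-student T0–T1 correlation of 0.6, stable class variance of 5% of the total, and time-specific class variance c. With w = 1 − 0.05 − c, the change-score ICC = 2c/[2c + 2w(1 − 0.6)], which goes into the formula of step 2.

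| c (share of total variance) | Change-score ICC | Type I error |
|---|---|---|
| 0 | 0 | 5.0% |
| 0.05% | 0.001 | 5.8% |
| 0.1% | 0.003 | 6.7% |
| 0.5% | 0.013 | 13.4% |
| 1% | 0.026 | 20.9% |
| 2% | 0.051 | 32.1% |

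**Step 5: the proposed design.** With 1:1 randomisation within class, class as a fixed effect, ICC 0.05 and no therapy-group effect, simulated type I error is 4.9% (20,000 replicates).

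A therapy-group effect would raise it. If all 55 treated students formed a single group with a shared effect of share g of the variance, R = 1 + 55g/(2 − g). For g = 1%, 2% and 5% the type I error is 8.2%, 11.5% and 20.4%.

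**The case against.** **The unit is open to another reading.** Pre-assignment Details screens individuals and then randomises, which could mean individual allocation. The two statements that name the class are the same sentences repeated, so they are not independent evidence. If students are in fact randomised individually, the confounding disappears. This stands as a condition on the conclusion. It does not remove the need for action: the class is the only unit the plan names, 55 per group fits either reading, and on the individual reading the two class statements would be wrong and need correcting.

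**A standard error can still be produced.** One could take an ICC from outside the trial and show results over a range. As a sensitivity analysis that is true. But the result then rests on the assumed ICC and not on the trial's data, and no such analysis is planned.

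**T0 helps.** It does, for class differences that stay constant, and with very small class-specific change the group-by-time test stays near 5% (5.8% and 6.7% in the first non-zero rows of step 4). But two classes give no means of showing that such change is small, and the named parameter, the difference in final means, does not remove even a stable difference. Baseline tests do not help either: a non-significant result does not show equality and says nothing about what happens after T0.

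**The sizes are illustrative.** Correct. Only the direction is certain.

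**Descriptive analysis is already listed.** It is, but next to superiority and a 0.05 level, so the plan does not limit itself to description. The terms confirmatory and causal are not the plan's own; they describe what a superiority test between randomised groups is ordinarily taken to mean.

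**Individual randomisation is not a complete cure.** Therapy-group clustering remains (step 5), and classmates in different arms may share content. Both stand as caveats. The first exists under class allocation too. The documents establish neither the size nor the direction of the second. Contamination would in any case be a reason to allocate clusters, not to allocate only one per arm.

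**Conclusion.** The concern holds and must be fixed before allocation. As written, the design cannot separate the intervention from the class that receives it, and the superiority tests keep their 0.05 level only if class variance is exactly zero (for group-by-time, the class variance of the change). Any non-zero class variance raises the false-positive rate. Over the assumed ICC range 0.001 to 0.10, the final-value test runs from 5.6% to 45.9%; the group-by-time test runs from 5.0% with a fully stable class difference to 32.1% in the most extreme scenario shown. Confidence in the finding is high. It rests on the plan's statement that the class is the unit; the percentages rest on assumed inputs.

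**What to change.** First reconcile Pre-assignment Details with Started and with Arm/Group Description in section 2, so that one unit of allocation is stated throughout.

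**Preferred.** Randomise enrolled students individually 1:1, stratified by class, after eligibility and T0, from a concealed computer-generated list. Include class as a fixed effect in the analysis. Record therapy-group membership and, if there are enough groups, allow for it in the intervention arm; with one or very few groups, state this as a limitation. This is a design change that needs an amended allocation procedure and a list. The change of unit needs no extra participants. The price is possible contamination between classmates.

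**If class allocation must stay.** Describe the study as a comparison of two intact classes with class confounded with treatment, add this to section 5, report estimates descriptively, and drop the superiority p-value and any causal claim. This costs text changes only.

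Several classes per arm would also restore degrees of freedom, but the plan has only two classes. With 110 students and an assumed ICC of 0.02, four clusters per arm would detect about 0.72 SD with 80% power, against about 0.53 SD under individual randomisation without therapy-group clustering.

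Timing matters. Baseline Measure Data and Outcome Data say the study has not started, and Recruitment Details plans recruitment from 1 May 2020. Once the classes have been allocated, only the text change remains available.

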### Completed \*

We will do follow-up post intervention, and the number in the follow-up will be recorded.

### Milestone Title [\*]

Before the intervention, we will measure the participants, and the stage is defined as T0.

We will do follow-up immediately after intervention, defined as T1.

### Reason Not Completed Type [\*]

We will record the exact reason (Adverse Event) why participants do not complete the study. The reason may be not interested, lack of efficacy, lost to follow-up, withdrawal by subject or others.

## 2. Baseline Characteristics

### Arm/Group Information \*

Chi-square test will be applied to figure out the difference of enumeration data between two groups. ANOVA will be applied to test the difference of measurement data between two groups. F values and  $\chi^2$  values will be displayed to show the baseline data are no different in two groups.

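### F and chi-square tests with 55 per arm cannot show that the two classes are alike at baseline, and the plan defines no protection against baseline imbalance

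*Combined protocol and SAP*

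**What the plan says.** Under 2. Baseline Characteristics, Arm/Group Information, two tests are planned: "Chi-square test will be applied to figure out the difference of enumeration data between two groups", and "ANOVA will be applied to test the difference of measurement data between two groups". The purpose follows: the "values will be displayed to show the baseline data are no different in two groups". The section gives no equivalence margin, no standardised differences and no rule for a significant result. The only significance level in the document is under P-Value: "P-Value will be set at 0.05".

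The arms are two classes of the same grade: "One will be randomly allocated as the intervention group, the other will be control group". The Pre-assignment Details table shows 55 in each group.

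For the outcomes, Estimation Parameter gives one entry, "Mean Difference (Final Values", with no covariate. The Method list has ANOVA, chi-squared and a two-sided t-test, and also "Other: repeated measurement of variance analysis within different measurements among different groups". It does not say which is primary. ANCOVA and adjustment for T0 are not mentioned anywhere.

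**The concern.** The baseline sentence announces its result in advance and treats a test of difference as evidence of sameness. A non-significant F or chi-square value means only that the data were compatible with no difference. In a small sample they are compatible with a sizeable difference as well.

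The inference is weak here because whole classes are allocated, one per arm. Randomising two classes does not balance their characteristics, and two classes may differ systematically. A reassuring baseline table could therefore lead readers to accept a T1 difference that partly reflects which class was which, or to miss an effect that a baseline gap has masked. T0 scores are collected on the same scales as the outcomes, so the plan could use them directly, but it does not say that it will.

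**Working it through.** **Inputs.** From the documents: 110 participants, 55 per arm (Pre-assignment Details); level 0.05 (P-Value), taken to apply to the baseline tests; two-sided, as for the t-test under Method; measurements at T0 and T1. Assumed, because the documents give no figures: the size of a true gap (in SD units), equal SDs, the T0-T1 correlation r (0.5 to 0.7), and independent students within a class.

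**The plan's own figure.** 55 + 55 = 110 checks. No power, effect size, SD or dropout rate is given, so the sample size cannot be reproduced further.

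**1. Largest observed gap that is non-significant.** ANOVA on two groups is the two-sided t-test. SE of the difference = √(2/55) = 0.1907 SD. With t(0.975, 108) = 1.982, the critical gap is 1.982 × 0.1907 = **0.378 SD**.

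**2. Power for a true gap d** (noncentral t, 108 df, noncentrality d/0.1907):

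| True gap (SD) | Power | Non-significant |
|---|---|---|
| 0.2 | 18% | 82% |
| 0.3 | 34% | 66% |
| 0.4 | 55% | 45% |
| 0.5 | 74% | 26% |

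Power of 80% needs about (1.960 + 0.842) × 0.1907 = 0.53 SD. Chi-square tests are no stronger: power is 18% for 50% v 60% and 31% for 10% v 20% (assumed percentages).

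**3. What showing sameness would take.** Two one-sided tests at 5% require the observed gap to lie at least 1.645 × 0.1907 = 0.314 SD inside the margin. With 55 per arm, a margin of 0.2 or 0.3 SD can never be met. For 80% power with a true difference of zero, margins of 0.2, 0.3 and 0.5 SD need about 429, 191 and 69 per arm.

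**4. Bias in the final-value difference when the test is passed.** Take a true T0 gap of 0.3 SD and no treatment effect. By normal approximation, the limits for passing are (−0.378 − 0.3)/0.1907 = −3.555 and (0.378 − 0.3)/0.1907 = 0.409. The chance of passing is Φ(0.409) − Φ(−3.555) = 0.66. Among trials that pass, the mean observed T0 gap is 0.3 + 0.1907 × (0.0007 − 0.3669)/0.6585 = 0.194 SD. The bias then depends on what happens to the class gap without treatment:

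- It shrinks to r × 0.3 by T1: bias = r × 0.194.
- It persists at 0.3: bias = 0.3 + r × (0.194 − 0.3) = 0.3 − 0.106r.

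| r | Bias, gap shrinks | Bias, gap persists |
|---|---|---|
| 0.5 | 0.10 SD | 0.25 SD |
| 0.6 | 0.12 SD | 0.24 SD |
| 0.7 | 0.14 SD | 0.23 SD |

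Simulation of 40,000 trials per setting gave the same values to within 0.01 SD.

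**5. The two ways of using T0, averaged over all trials** (same 0.3 SD gap):

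| r | ANCOVA, shrinks | ANCOVA, persists: (1 − r) × 0.3 | Change, shrinks: −(1 − r) × 0.3 | Change, persists |
|---|---|---|---|---|
| 0.5 | 0 | 0.15 SD | −0.15 SD | 0 |
| 0.6 | 0 | 0.12 SD | −0.12 SD | 0 |
| 0.7 | 0 | 0.09 SD | −0.09 SD | 0 |

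**6. Precision.** Adjusting for T0 multiplies the SE by √(1 − r²): 0.1907 × 0.866 = 0.165 SD at r = 0.5, and 0.1907 × 0.714 = 0.136 SD at r = 0.7.

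**The case against.** The strongest reply is that the baseline sentence describes a display. No decision hangs on it, no threshold is attached to it, and baseline P-values do not alter the T1 estimate. That is right as far as it goes: both the 0.05 level and the reading that non-significance will count as proof are inferred. But the stated purpose of the display is to show no difference, and no threshold would make these tests able to do that.

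A reader might infer several stronger things that the documents do not support.

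- *That the baseline tests are the plan's only protection.* The group-by-time term of the listed repeated-measures ANOVA compares changes from T0 to T1, so it uses T0. The fair criticism is that its role is undefined and it does not match the final-values estimate.
- *That the T0 scale scores are left out of the baseline comparison.* Baseline Measure Title does not list them, but Baseline Measure Information has an open-ended list, and ANOVA is to be applied to measurement data generally. They are unlisted, not excluded.
- *That real imbalances in general would be declared absent.* Gaps of about 0.53 SD or more would usually be flagged. The problem concerns small to moderate ones.
- *That baseline adjustment cures the problem.* ANCOVA is unbiased in one scenario above and the change analysis in the other, and the documents cannot say which applies. Neither removes the confounding of class with arm.

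**Conclusion.** The concern holds in a limited form. The stated inference is wrong, and 55 per arm cannot support it: about two-thirds of true 0.3 SD gaps would be non-significant. Because the estimate is an unadjusted final-value difference and the analysis that uses T0 has no assigned role, the plan has no defined protection against baseline imbalance.

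The consequence for a 0.3 SD gap that passes the test is a bias of about 0.10 to 0.14 SD if the gap shrinks with the correlation, or about 0.23 to 0.25 SD if it persists. These figures rest on the assumed gap, correlations of 0.5 to 0.7 and independent students. The power figures and the critical gap need only the arm size, the inferred 0.05 level, equal SDs and independence. This should be corrected before analysis. It does not show that the classes will in fact differ, or by how much.

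**What to change.** 1. Delete the statement that F and chi-square values will show no baseline difference.
2. Tabulate baseline variables by arm, explicitly including the T0 scores of all four scales, as mean (SD) or n (%) with standardised differences and no P-values.
3. Name as the analysis of each scale the T1 mean difference adjusted for the T0 score of that scale (ANCOVA), whatever imbalance is observed.
4. Keep the repeated-measures (change) analysis as a prespecified sensitivity analysis, because ANCOVA leaves about 0.09 to 0.15 SD of bias if a 0.3 SD class gap persists. Report both results, and discuss any disagreement between them.
5. State as a limitation that, with one class per arm, no baseline adjustment removes the confounding of class with intervention.

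The cost is wording only. T0 scores are already to be collected, so no new data are needed.
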